#### Hgb Values for Efficacy Analyses

correlation coefficient.

#### Scatter plot of Change from Baseline in Hgb at Week 4 vs. Candidate Covariates

- The following scatter plot figures will be produced for overall and dialysis status groups:
  - Change from baseline in Hgb at Week 4 vs. Body Weight at Screening
  - Change from baseline in Hgb at Week 4 vs. Baseline Hgb
- Vertical axis will indicate the change from baseline in Hgb (g/dL) at Week 4, horizontal axis will indicate the candidate covariates; body weight (kg) at screening or baseline Hgb (g/dL).

#### Scatter plot of Mean Dose during Week 12 to 24 vs. Candidate Covariates

- The following scatter plot figures will be produced for overall and dialysis status groups:
  - Mean Dose during Week 12 to 24 vs. Body Weight at Screening
  - Mean Dose during Week 12 to 24 vs. Baseline Hgb
- Vertical axis will indicate the mean dose (mg), horizontal axis will indicate the candidate covariates; body weight (kg) at screening or baseline Hgb (g/dL).
- Mean dose will be calculated from the arithmetic mean using the latest 3 exposure records (i.e., for completers Week 12, 16, and 20), which are based on the prescribed doses and the scheduled visits.
- Subjects who has less than 3 dosing records will be excluded from the figures.
- Mean dose during Week 12 to 24 will also be summarized and listed.

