7.1. Time and Events Table

Time and Events Tables are provided in Table 6 and Table 7 for the overall study and for pharmacokinetic assessments. For subjects on dialysis twice or more per week, throughout the study period, including the screening, treatment and follow-up periods, the study visit days should occur on the first dialysis session day of the week (e.g., if Monday-Wednesday-Friday schedule, the study visit should be on Monday). Visit days are counted from the day of first dose of study treatment (Day 1). To allow for a flexible schedule, the allowable window for Screening Visit will be “4 weeks \pm 7 days prior to Day 1”, and that for the visits after Day 1 will be “ \pm 3 days”. In any case, the study visit should occur on the first dialysis session day of the week. Unless otherwise specified, all assessments should occur before dialysis on the day.

Table 6 Time and Events Table

Period	Screening		Treatment							Follow-up	
Visits All assessments pre-dialysis, unless noted.		Week -4	Day 1	Week 4	Week 8	Week 12	Week 16	Week 20	Week 24	Early withdrawal ¹⁰	2–4 weeks after Week 24 or early withdrawal
Allowable window (days)		±7	-	±3	±3	±3	±3	±3	±3	-	±3
Informed consent	X										
Inclusion/exclusion		X	X								
Medical history, demography, height, body weight ¹		X									
Interactive Web Recognition System (IWRS) call		X	X	X	X	X	X	X	X	X	X
Study medication dispensing ²			X	X	X	X	X	X			
Study medication compliance				X	X	X	X	X	X	X	
Vital signs (before and after dialysis) ³		X	X	X		X			X	X	X
Ophthalmology examination ⁴		X ¹¹				↔	↔	↔	↔	↔	
ECG		X				X			X		
HemoCue Hgb			X	X	X	X	X	X	X		
Hematology		X ¹²	X	X	Hgb only	X	Hgb only	Hgb only	X	X	X
Clinical chemistry		X	X	X		X			X	X	X
Ferritin, TSAT		X	X	X		X			X	X	
Serum iron, TIBC, Unsaturated iron Binding Capacity (UIBC), serum transferrin, hepcidin			X	X		X			X	X	
Serum pregnancy test ⁵		X	X	X		X			X	X	X
Estradiol ⁵ , FSH ⁶		X									
Pharmacokinetics ⁷						X			X		
Intact Parathyroid Hormone (iPTH)			X	X		X			X		
Genetics sample ⁸			X								
Adverse event assessment ⁹											→
Concomitant medication assessment											→

1. Body weight is measured after dialysis.
2. If a subject visit the study site only to receive study medication, only the IWRS call, study medication dispensing, and study medication compliance will be required
3. At visits without dialysis, only one measurement of each parameter will be obtained.
4. Ophthalmology exams should be conducted at the following time points.

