#### Dose Adjustment

#### Dose adjustment algorithm

- Dose Adjustment algorithm will be based on HemoCue Hgb values at scheduled visits. No Hgb values measured at unscheduled visits will be included.
- Dose will be derived from prescribed dose recorded in eCRF, not actual dose associated with container numbers.
- The following table illustrates the algorithm using analysis flags as below:
  - (FL\_A): Adjustment flags will be counted if prescribed dose recorded in eCRF is changed from that of the previous visit.
  - (FL\_B): Over 13 g/dL flags will be counted if HemoCue Hgb >13 g/dL is observed.
  - (FL\_C): Interruption flags will be counted if prescribed dose recorded in eCRF is zero. Treatment durations will be calculated based on the following formula:
    - Duration (days) = Treatment Stop Date Treatment Start Date + 1

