#### Illustration of dose adjustment algorithm

	Treatment		HemoCue		(FL_A)	(FL_B)	(FL_C)
Visit	Start date/		Hgb	Dose	Adjust-	Over	Inter-
(Example)	Stop date	Duration	(g/dL)	(mg)	ment	13 g/dL	ruption
Day 1	01FEB2017/	29	11.1	4	Ν	Ν	Ν
-	01MAR2017						
Week 4	02MAR2017/	14	11.4	4	Ν	Ν	Ν

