# 10.7. Appendix 7: Premature Withdrawals & Handling of Missing Data

#### 10.7.1. Premature Withdrawals

Element	Reporting Detail
General	
 
Subject study completion (i.e. as specified in the protocol) was defined as completing all periods of the study including the follow-up visit.
 
The study will be completed with the last subject's last study visit
 
Withdrawn subjects will not be replaced in the study.
 

	
 
All available data from subjects who were withdrawn from the study will be listed and all available planned data will be included in summary tables and figures, unless otherwise specified.
 

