## 10.15. Appendix 15: Example Mock Shells for Data Displays

These are provided with separated documents.

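### The Week 12 to 24 mean dose averages in doses from before Week 12 for subjects who stop treatment early

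*SAP*

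**What the plan says.** The definition is in SAP 10.6.3, under the scatter plots of mean dose against body weight and baseline Hgb: "Mean dose will be calculated from the arithmetic mean using the latest 3 exposure records (i.e., for completers Week 12, 16, and 20"). It uses prescribed doses at scheduled visits. Two further bullets matter. One is the only exclusion: "Subjects who has less than 3 dosing records will be excluded from the figures". The other extends the variable beyond the plots: "Mean dose during Week 12 to 24 will also be summarized and listed". SAP 8.1.2 repeats that the mean will be summarised, and SAP 10.14 places it in Tables 2.41 and 2.42 and Figures 2.21 to 2.24, all on the All Treated Subjects population.

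For withdrawn subjects, SAP 10.7.1 provides that "all available planned data will be included in summary tables and figures, unless otherwise specified".

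The row "Study medication dispensing" in Protocol Table 6 is marked at Day 1 and Weeks 4, 8, 12, 16 and 20, and not at Week 24. Under Protocol 6.3 the Day 1 dose is fixed at 4 mg and doses can change every four weeks from Week 4.

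**The concern.** The name of the variable gives a calendar window, but its definition counts backwards from the last record. The two agree for a subject who has the Week 12, 16 and 20 records. For a subject who stops before the Week 20 dispensing, the count reaches back before Week 12. If the last record is Week 8, it reaches the fixed starting dose, and a value is reported for a window in which the subject was prescribed nothing.

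The RAP amendment table says these plots were added to help judge the starting or maintenance dose. For a subject being titrated upward when treatment stops, the rule understates the in-window dose; for one being titrated downward, it overstates it. At stake are one descriptive row in two tables, four exploratory plots and a listed value.

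**Working it through.** **Inputs.** Dispensing visits: Protocol Table 6. Dose steps 1, 2, 4, 6, 8, 12, 18, 24 mg and the 4 mg start: Protocol 6.3. Planned numbers: Protocol 4.3 and Table 1.

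**1. Planned numbers.** 22 x (1 - 0.20) = 17.6, which the protocol gives as 17 completers. Table 1 has 20 completing Week 4 and 17 completing Week 24, so 20 - 17 = 3 leave in between, or 3/20 = 15%. Someone leaving before the Week 8 dispensing has fewer than three records. Someone leaving after the Week 20 dispensing is handled correctly. Only the 12 weeks from Week 8 to Week 20 matter, so the affected number is 0 to 3. If the times of leaving were uniform over the 20 weeks (my assumption), it would be 3 x 12/20 = 1.8, about 2.

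**2. Records that enter the mean.**

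| Last record | Records averaged | Starting in Week 12 to 24 |
|---|---|---|
| Week 8 | Day 1, Weeks 4, 8 | 0 of 3 |
| Week 12 | Weeks 4, 8, 12 | 1 of 3 |
| Week 16 | Weeks 8, 12, 16 | 2 of 3 |
| Week 20 | Weeks 12, 16, 20 | 3 of 3 |

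**3. Size.** Difference = mean of the last three doses, minus the mean of the doses from Week 12 onward. All paths start at 4 mg and go up one step, stay, or go down one step at each visit, without interruption.

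- Last record Week 12 (26 paths). Lowest: 6, 8, 12 mg gives (6 + 8 + 12)/3 - 12 = 8.67 - 12 = -3.33 mg. Highest: 6, 4, 2 mg gives (6 + 4 + 2)/3 - 2 = 4 - 2 = +2.00 mg.
- Last record Week 16 (75 paths). Lowest: 8, 12, 18 mg gives (8 + 12 + 18)/3 - (12 + 18)/2 = 12.67 - 15 = -2.33 mg. Highest: 8, 6, 4 mg gives (8 + 6 + 4)/3 - (6 + 4)/2 = 6 - 5 = +1.00 mg.
- Last record Week 8 (9 paths). There is nothing to compare with. The reported value runs from (4 + 2 + 1)/3 = 2.33 mg to (4 + 6 + 8)/3 = 6.00 mg.
- Unchanged dose, last record Week 12 or 16: the difference is 0.

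**4. The SAP's own dose example.** The table headed "Illustration of dose adjustment algorithm" has 4, 4, 2, 0, 1, 0 mg from Day 1 to Week 20. With all records, the rule gives (0 + 1 + 0)/3 = 0.33 mg, which is the in-window mean. Cutting the path short is my hypothetical:

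- at Week 16, (2 + 0 + 1)/3 = 1.00 against (0 + 1)/2 = 0.50 mg;
- at Week 12, (4 + 2 + 0)/3 = 2.00 against 0 mg;
- at Week 8, (4 + 4 + 2)/3 = 3.33 mg with no in-window dose.

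This shows arithmetic only. The example is a programming illustration, and its Day 1 Hgb of 11.1 g/dL lies outside the entry range.

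**The case against.** **The rule is disclosed and may be a deliberate late-dose proxy.** The remark about completers tells the reader that other subjects contribute other records, and the last three doses are a reasonable proxy for maintenance dose. That stands as a defence of the rule, but not of the name. A footnote may exist, since the mock shells are separate: "These are provided with separated documents".

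**The exclusion might mean fewer than three records inside the window.** That would cure the figures. The text names no window, however, and the remark about completers points the other way. The tables and listing would still be uncovered. For subjects with one or two records, a missing value is the natural reading there, but it is not stated.

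**The ranges are extremes.** This is correct; they are not expected values. I left interruptions out of the ranges. The SAP codes an interruption as a dose record of zero ("Interruption flags will be counted if prescribed dose recorded in eCRF is zero"), so it does not shift the count of records, but it can widen the upper limit. For example, 6, 8, 0 mg gives 14/3 = 4.67 against 0 mg. Under Protocol Table 5 that path needs Hgb below 10.0 g/dL at Week 8 and above 13.0 at Week 12.

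**Little depends on it.** This also stands. By-visit doses, the dose distribution, subject profiles and the exposure listing show every dose.

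**A stronger reading to avoid.** A reader might infer that any missing Week 12 or Week 16 record causes the same error in a subject who stays on treatment. The documents do not support this. Exposure records are intervals with start and stop dates (SAP 10.6.2 and the dose example). If the dose is unchanged at the missed visit, the Week 8 dose is still in force there. With Week 12 missing and 8, 12, 18 mg at Weeks 8, 16 and 20, the rule gives 38/3 = 12.67 mg, and so do the doses in force at Weeks 12, 16 and 20. With Week 16 missing, the error is (Week 8 dose - Week 12 dose)/3. Its limits are (8 - 12)/3 = -1.33 and (8 - 6)/3 = +0.67 mg.

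**Conclusion.** The definition does not match its label for subjects who stop treatment with a last scheduled record at Week 8, 12 or 16, and nothing else in the SAP repairs this. The extremes without interruption are -3.33 to +2.00 mg (last record Week 12) and -2.33 to +1.00 mg (Week 16). At Week 8 a value of 2.33 to 6.00 mg is reported with no in-window dose.

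The count of about 0 to 3 subjects rests on the planning figures and is not a bound, since enrolment is stated as a minimum. The ranges assume one-step changes from 4 mg.

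The point is minor. It would be wrong to infer that every non-completer is affected, because one who stops after the Week 20 dispensing is not. It would also be wrong to infer that an endpoint is at risk: no listed endpoint uses the variable, and SAP 10.10.1 limits the covariate plots to exploratory use.

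**What to change.** Choose one of two changes in SAP 10.6.3.

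- **Keep the window.** For subjects who stop early, average only the prescribed doses from Week 12 onward, set the value to missing if there are none, and report n. If a scheduled visit is missed while treatment continues, use the prescribed dose in force over that interval; do not drop it. Simply averaging whichever records exist would be worse than the present rule when Week 12 is missing. In the 8, 12, 18 mg case it would give (12 + 18)/2 = 15 instead of 12.67 mg. Downside: a few subjects drop out and some means rest on one or two records.
- **Keep the rule.** Rename the variable as the mean of the last three prescribed doses. Downside: the value no longer refers to a fixed calendar window.

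In either case, apply one inclusion rule to figures, tables and listing. The cost is a short change to the SAP text with a small derivation change, or new labels in Tables 2.41 and 2.42 and Figures 2.21 to 2.24. No new data are needed.

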#### Dose Adjustment

#### Dose adjustment algorithm

- Dose Adjustment algorithm will be based on HemoCue Hgb values at scheduled visits. No Hgb values measured at unscheduled visits will be included.
- Dose will be derived from prescribed dose recorded in eCRF, not actual dose associated with container numbers.
- The following table illustrates the algorithm using analysis flags as below:
  - (FL\_A): Adjustment flags will be counted if prescribed dose recorded in eCRF is changed from that of the previous visit.
  - (FL\_B): Over 13 g/dL flags will be counted if HemoCue Hgb >13 g/dL is observed.
  - (FL\_C): Interruption flags will be counted if prescribed dose recorded in eCRF is zero. Treatment durations will be calculated based on the following formula:
    - Duration (days) = Treatment Stop Date Treatment Start Date + 1

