Dose level (mg) at each assessment visit			Y	Y		
by Dialysis Status			N			
>13.0 g/dL [3]			Y			
Duration (days) of treatment interruption due to Hgb			Y			
>13.0 g/dL [3]						
by Dialysis Status						
Dose adjustment			Y			
Dose adjustment			Y			
by Dialysis Status						
Number (%) of subjects with each dose level at each			Y			
assessment visit						
Number (%) of subjects with each dose level at each			Y			
assessment visit						
by Dialysis Status						
Number of dose adjustment to reach the lower Hgb target			Y			
Hgb level (10.0 g/dL)			N			
Number of dose adjustment to reach the lower Hgb target			Y			
Hgp level (10.0 g/dL)						
by Dialysis Status						
Uther				V		
Scaller plot of change from baseline in Hgb at week 4 Vs.				ľ		
Cantuluate Covariates [0]				V		
Scaller plot of mean dose vs. candidate covariates [6]		1		Υ		

NOTES :

[1] Not only within the target range, but also subjects with above and below target range will be assessed.
[2] Time to first reach the lower target Hgb level will be estimated by Kaplan-Meier method using P25, median and P75. Subjects who could not reach lower target will be regarded as censored.

Endpoint / Parameter/ Display Type			Abso	olute		
	Stats A	nalysis	Summary		Individual	
	Т	F	Т	F	F	L

[3] On-therapy Hgb values observed in scheduled visits will be included. On-therapy Hgb values observed in unscheduled visits will be included if specified (see Section 8.1.2)

[4] Based on literature review the distributions of TSAT and hepcidin are skewed and require a log-transformation.

[5] Summaries for dose adjustment will be based on HemoCue Hgb values including those of unscheduled visits.[6] Figures will include the candidate covariates of body weight and baseline Hgb, and will be produced for overall and dialysis status groups.

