#### • Dose adjustment

The dose adjustment algorithm is described in Section 10.6.3, based on HemoCue Hgb values including those in both scheduled and unscheduled visits

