#### Duration (days) of treatment interruption due to Hgb >13.0 g/dL

The number and percentage of subjects who have a period of treatment interruption due to Hgb >13.0 g/dL will be summarized. On subjects who have a period of treatment interruption due to Hgb >13.0 g/dL, the duration (in days) of treatment interruption due to Hgb >13.0 g/dL per subject will be summarized using mean, standard deviation, minimum, P25, median, P75, and maximum. Hgb values observed in both scheduled and unscheduled visits will be counted in the summary. This will be also summarized by baseline dialysis status.

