#### 204716

#### CONFIDENTIAL

Dose A	djustment								
		15MAR2017							
	Week 8	02APR2017/	30	11.8	2	Y	N	N	
		01MAY2017							
	Week 12	02MAY2017/	31	13.4	0	Y	Y	Y	
		01JUN2017		44.0		N (			
	Week 16	02JUN2017/ 01JUL2017	30	11.6	1	Y	N	N	
	Week 20	02JUL2017/	31	12.7	0	Y	Ν	Y	
		01AUG2017							
	Week 24	-	-	12.3	-	-	Ν	-	

 
'Dose adjustment'
 
Duration (days) of treatment interruption due to Hgb >13 g/dL
 
									
Calculation of duration of treatment interruption due to Hgb >13 g/dL will be based on the above									
algorithm and the below formula.									

 
Duration (days) = Sum of [Duration]n
 
									
	where								
	[Duration]₀ represents exposure duration at visit n.								
If over 13 g/dL flag (FL_B) = 'Y' and interruption flag (FL_C) = 'Y':									

 
Duration (days) = Treatment Stop Date - Treatment Start Date + 1
 
									
If else:									

 
Duration (days) = 0
 
									
Frequency of dose adjustment									
Calculation of frequency of dose adjustment will be based on the above algorithm.									

 
Number of dose adjustment will be counted for each subject as follows:
 
									

 
Counts of adjustment flag = 'Y'
 
									
Number of dose adjustment to reach the lower Hgb target (10.0 g/dL)									
Number of dose adjustment to reach the lower Hgb target will be counted for each subject as follows									
• Counts of adjustment flag ='Y' at visits before Date to reach the lower Hgb target, including a record which firstly achieved the lower Hgb target.									

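### SAP 10.6.3 leaves out unscheduled HemoCue values that SAP 8.1.2 and Table 4 require, so interruption due to Hgb >13 g/dL can be understated

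*SAP*

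**What the plan says.** Three places in the SAP bring unscheduled HemoCue values in.

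- Table 4, note [5]: "Summaries for dose adjustment will be based on HemoCue Hgb values including those of unscheduled visits".
- Section 8.1.2, under Dose adjustment: "The dose adjustment algorithm is described in Section 10.6.3, based on HemoCue Hgb values including those in both scheduled and unscheduled visits".
- Section 8.1.2, under the duration of interruption due to Hgb >13.0 g/dL: "Hgb values observed in both scheduled and unscheduled visits will be counted in the summary".

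Section 10.6.3 takes them out. It says "Dose Adjustment algorithm will be based on HemoCue Hgb values at scheduled visits" and then "No Hgb values measured at unscheduled visits will be included". It goes on to define three flags:

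- FL_A: the prescribed dose differs from that of the previous visit.
- FL_B: HemoCue Hgb is above 13 g/dL.
- FL_C: the prescribed dose is zero.

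Interruption days due to Hgb >13 are summed over records on which FL_B and FL_C are both Y; every other record adds 0. Frequency of dose adjustment is the count of FL_A = Y, and the SAP ties it to the same algorithm: "Calculation of frequency of dose adjustment will be based on the above algorithm". Both quantities are listed as secondary endpoints in protocol Section 3 and SAP 2.2.

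**The concern.** Section 8.1.2 sends the reader to 10.6.3 for the algorithm and describes it as including unscheduled values, while 10.6.3 excludes them. A programmer cannot follow both.

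The general rule in SAP 10.5.3 does not settle it. By default it leaves unscheduled visits out of summary tables, except where a section specifies otherwise, and Table 4 and 8.1.2 do specify otherwise. SAP 10.5.3 also promises a description of how a summary that includes unscheduled visits will be produced, and 10.6.3 gives none.

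At stake is one secondary summary, reported as the number (%) of subjects interrupted for Hgb >13 and, among those subjects, the days. With about 22 subjects and a duration summary restricted to those interrupted, a single subject can be a large part of that summary, or all of it.

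**Working it through.** **1. The SAP's own illustration (10.6.3, scheduled visits only).** Duration = stop date − start date + 1.

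| Visit | Days | HemoCue (g/dL) | Dose (mg) | FL_A | FL_B | FL_C |
|---|---|---|---|---|---|---|
| Day 1 | 29 | 11.1 | 4 | N | N | N |
| Week 4 | 14 | 11.4 | 4 | N | N | N |
| Week 8 | 30 | 11.8 | 2 | Y | N | N |
| Week 12 | 31 | 13.4 | 0 | Y | Y | Y |
| Week 16 | 30 | 11.6 | 1 | Y | N | N |
| Week 20 | 31 | 12.7 | 0 | Y | N | Y |

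All six durations and all flags reproduce from the dates, Hgb values and doses. The totals are 4 adjustments and 31 days of interruption due to Hgb >13 (Week 12 only).

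**2. What one unscheduled record could do.** The Week 4 record stops on 15MAR2017 and the Week 8 record starts on 02APR2017. That leaves 16MAR2017 to 01APR2017, or 17 days, uncovered. Assume, although the SAP does not say so, that one unscheduled record fills the gap.

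| Assumed unscheduled record | Adjustments | Days due to Hgb >13 |
|---|---|---|
| 13.2 g/dL, 0 mg | 5 | 31 + 17 = 48 |
| 12.4 g/dL, 2 mg | 4 | 31 |
| 11.5 g/dL, 4 mg | 4 | 31 |

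The extra 17 days need both the Hgb value and the zero dose. The step from 4 to 5 adjustments comes from the dose record alone (4 to 0 mg, then 0 to 2 mg), because no Hgb value enters FL_A.

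**3. A hold that starts between visits (hypothetical).** An unscheduled HemoCue at Week 10 reads 13.4 g/dL and the prescribed dose becomes 0 mg. At Week 12 the value is 12.4 g/dL and the dose is still 0 mg.

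- Under 10.6.3, the Week 10 value is not used. At Week 12, FL_B = N and FL_C = Y, so 0 days are counted and the subject is not classed as interrupted for Hgb >13.
- Under 8.1.2, with the matching dose record, FL_B and FL_C are both Y from Week 10 to Week 12: 2 × 7 = 14 days. The Week 12 record still adds 0, because 12.4 is not above 13. The total is about 14 days and the subject is counted.
- If the Week 12 value were itself above 13 at 0 mg, 10.6.3 would flag the subject from Week 12. Only the roughly 14 days before it would be lost.

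**4. Effect on the percentage.** With 22 treated subjects, one subject is 1/22 = 4.5 percentage points.

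**The case against.** The study is descriptive, with no hypothesis test, and the primary endpoints do not use this algorithm. Protocol 6.3 bases dose changes on HemoCue values taken every 4 weeks, so a hold that starts between visits falls outside the planned schedule and may be rare. That stands as a limit on size. It does not remove the conflict, because the SAP allows for such data: 10.6.5 takes the PK dose level from visits that include unscheduled ones.

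A reader might infer more than the documents support.

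- *Both secondary endpoints give different results under the two rules.* Table 4 note [5] and 8.1.2 do cover all dose-adjustment summaries, but FL_A compares prescribed doses only. Including or excluding Hgb values cannot change it.
- *Such a subject always contributes zero.* Only if no scheduled HemoCue value during the hold exceeds 13.
- *The >13 g/dL table and the interruption table disagree because of this rule.* The >13 count does include unscheduled values. However, it uses central-laboratory Hgb first, with HemoCue as the fallback (SAP 8.1.3 and 10.6.3), so the two tables could differ even with identical visit rules.
- *Safety information on high Hgb is lost.* Unscheduled values above 13 remain in the >13 count and episodes (8.1.2) and in the listings (10.5.3). Only the attribution of interruption days is affected.

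**Conclusion.** The contradiction is explicit and stands in the current SAP text. Its numerical effect falls on one secondary endpoint, interruption due to Hgb >13 g/dL, where following 10.6.3 can understate both the number (%) interrupted and the days. The figures of about 14 days and 4.5 points assume one such subject, 22 treated subjects and an unscheduled dose record that matches the Hgb value. They are illustrations, since the documents give no number of unscheduled HemoCue values.

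For frequency of dose adjustments, and for the number of adjustments to reach 10.0 g/dL, which uses the same flag, the open question is whether an unscheduled dose record is a visit. It would be wrong to read the 14 days as a minimum: hold days recorded against a later value of 13 or below are dropped by the FL_B and FL_C formula itself, a separate matter. This should be corrected, but it does not threaten the main conclusions.

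**What to change.** In SAP 10.6.3, replace the two scheduled-only sentences. FL_B and the interruption duration should use HemoCue values and the matching prescribed-dose records from scheduled and unscheduled visits, ordered by date. This agrees with Table 4 note [5] and both statements in 8.1.2.

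In the same place, state whether an unscheduled prescribed-dose record counts as a visit for FL_A. That is a separate decision, because it changes what the previous visit means and so can change the adjustment count. Adding one unscheduled record to the illustration would show the intended result. By-visit dose tables can stay on scheduled visits.

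The cost is a wording change and a small amount of programming on recorded data. It should be settled before database freeze, by which point the SAP synopsis requires analysis decisions to have been made. This concerns which data enter the analysis, and no dosing rule changes.
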